10.1.4.2 Data Sharing for Secondary Research

Data from this study may be used for secondary research. All of the individual participant data collected during the trial will be identified by a coded number that is linked to a participant through a code key maintained at the clinical site. The code key is kept confidential and will not be transmitted off site. All of the individual participant data collected during the trial will be made available after deidentification. The Protocol, Statistical Analysis Plan, and Analytic Code will also be made available. These data will be available immediately following publication, with no end date.

The investigator may request removal of data on individual study participants from NIH data repositories in the event that a research subject withdraws or changes his or her consent. However, some data that have been distributed for approved research use cannot be retrieved.

10.1.5 Key Roles and Study Governance

This study is sponsored by DMID. The Principal Investigator, DMID Clinical Project Manager, DMID Medical Officer, and DMID Scientific Lead are listed on the cover page. Other study team members and roles are listed in the Manual of Procedures (MOP).

10.1.6 Safety Oversight

The SRC Safety Review Committee consists of the PI at each participating site (or their delegate), representatives of the sponsor (at least the Medical Monitor and the Medical Officer), representatives of the manufacturer (at least the Medical Lead or delegate), and representatives of the SDMCC. The SRC will review the data required to allow progression from cohort to cohort. These reviews occur as described in the study design section, [Section 4.1](#). Ad hoc reviews may also be called for by the investigators or sponsor. Decisions are dependent on the failure to meet halting criteria when the required follow-up data are available. The SRC deliberations may occur by teleconference, videoconference, or email. If the SRC determines that the study data have met the criteria necessary to begin a subsequent cohort, the sponsor will notify the sites of the determination. If the SRC is unable to determine that the criteria necessary to begin a subsequent cohort have been met, or if halting rules have been met, the SMC will convene.

The SMC is an independent group of at least 3 experts that monitors participant safety and advises DMID. SMC members will be separate and independent of study personnel participating in this trial and should not have scientific, financial, or other conflicts of interest related to this trial. The SMC will consist of members with appropriate expertise to contribute to the interpretation of data from this trial. A quorum will consist of a simple majority.

The SMC will hold an organizational meeting prior to enrollment. At this meeting, the SMC will review the charter, protocol, ICF, and safety report template.

The SMC will conduct the following reviews:

1. Review of safety if a halting rule is met

2. Review of safety if the SRC requests a review
3. Review of safety, tolerability, and trial progress at the following times: after the first season of vaccinations, after the second season of vaccinations, at the conclusion of the trial
4. Ad hoc review as needed when requested by the sponsor, investigators, or SMC

Procedures for SMC reviews/meetings will be defined in the SMC charter. The SMC will review applicable data including, but not limited to, enrollment, demographics, dosing, data, laboratory data, and safety data at scheduled time points during this trial as defined in the SMC charter. The SMC will review blinded aggregate data in the open session of the SMC meetings. Unblinded data (grouped by treatment) may be reviewed in the closed session only. When possible, these data will be “aliased” in that the SMC will review the data by group, but the identity of the group will not be divulged. The SMC may, if necessary, review grouped data in which the identities of the groups are divulged.

Additional data may be requested by the SMC, and interim statistical reports may be generated as deemed necessary and appropriate by DMID. As an outcome of each review/meeting, the SMC will make a recommendation as to the advisability of proceeding with study drug administration, and to continue, modify, or terminate this trial.

10.1.7 Clinical Monitoring

Site monitoring is conducted to ensure that the rights and well-being of trial participants are protected, that the reported trial data are accurate, complete, and verifiable, and that the conduct of the trial is in compliance with the currently IRB/IEC-approved protocol/amendment(s), ICH GCP, and applicable regulatory requirement(s). Clinical monitoring also verifies any critical study procedures are completed following specific instructions in ancillary documents referenced in the protocol such as a Manual of Procedures.

Monitoring for this study will be performed by DMID. Details of clinical site monitoring are documented in a Clinical Monitoring Plan (CMP). The CMP describes in detail who will conduct the monitoring, at what frequency monitoring will be done, at what level of detail monitoring will be performed, and the distribution of monitoring reports. Monitoring visits will include, but are not limited to, review of regulatory files, accountability records, eCRFs, ICFs, medical and laboratory reports, site study intervention storage records, training records, and protocol and GCP compliance. Site monitors will have access to each participating site, study staff and all study documentation according to the DMID-approved CMP. Study monitors will meet with all participating site PIs to discuss any problems and outstanding issues and will document site visit findings and discussions.

10.1.8 Quality Assurance and Quality Control

To ensure the reliability of study data, the site will develop a Clinical Quality Management Plan (CQMP). The CQMP will describe routine internal quality control (QC) and quality assurance (QA) activities for the purposes of measuring, documenting, and reporting study conduct, protocol adherence, human participant protections, and reliability of the protocol-driven data collected. A process for addressing in a timely manner any data quality issues (for example,

collecting, recording, and reporting data), systemic issues (for example, protocol conduct, non-compliance, human participant protections), and implementation of Corrective and Preventative Action (CAPA) procedures.

The SDMCC will implement quality control procedures beginning with the data entry system and generate data quality control checks that will be run on the database. Any missing data or data anomalies will be communicated to the site(s) for prompt clarification and resolution.

10.1.9 Data Handling and Record Keeping

10.1.9.1 Data Collection and Management Responsibilities

Clinical research data (including, but not limited to, AE/SAEs, concomitant medications, medical history, physical assessments), and clinical laboratory data will be abstracted from the source documentation and/or collected on source document worksheet by study personnel then entered into eCRFs via a 21 CFR Part 11-compliant internet data entry system provided by the study data coordinating center. Alternatively, direct data entry may be employed. The data system includes password protection and internal quality checks, such as automatic range checks, to identify data that appear inconsistent, incomplete, or inaccurate.

Data collection is the responsibility of the study personnel at the participating clinical study site under the supervision of the site principal investigator. During the study, the site principal investigator must maintain complete and accurate documentation for the study.

The data coordinating center for this study will be responsible for data management, quality review, analysis, and reporting of the study data. The IND sponsor is responsible for review of data collection tools and processes, and review of data and reports. Adverse events will be coded according to the MedDRA dictionary version 23.0 or higher. At the end of the study, a copy of all datasets including annotated case report forms and data dictionary will be provided to DMID.

A separate SDSP will be developed which describes the technical recommendations for the submission of human study data and related information in a standardized electronic format throughout product development.

10.1.9.2 Study Record Retention

Study-related records, including the regulatory file, study product accountability records, consent forms, participant source documents and electronic records should be maintained for a period of 2 years following the date a marketing application is approved for the investigational product for the indication for which it is being investigated; or, if no application is to be filed or if the application is not approved for such indication, until 2 years after the investigation is discontinued and FDA is notified. These documents should be retained for a longer period, however, if required by local policies or regulations. No records will be destroyed without the written consent of DMID. Consent forms with specimen retention linked to identifiable specimens will be maintained for as long as the specimens remain in identifiable format, and a minimum of three years after use of the identifiable specimens in nonexempt human participant research.

10.1.9.3 Source Records

Source data are all information, original records of clinical findings, observations, or other activities documented in a clinical trial necessary for the reconstruction and evaluation of the trial. Each participating site will maintain appropriate medical and research records for this trial, in compliance with ICH GCP, regulatory, and institutional requirements. Data recorded in the electronic case report form (eCRF) derived from source documents should be consistent with the data recorded on the source documents. All source documents should be completed in a neat, legible manner to ensure accurate interpretation of data.

For this trial, investigators may, when necessary, use the electronic medical record as source data, but most of the information required will be collected from the parents/guardians and as part of the conduct of the study.

10.1.10 Protocol Deviations

A protocol deviation is any noncompliance with the clinical trial protocol, any process that is noted in the protocol and refers to details in the MOP, or GCP requirements.

Noncompliance may be either on the part of the participant, the investigator, or the study site staff. Following a deviation(s), corrective actions should be developed by the site and implemented promptly. All individual protocol deviations will be addressed in participant study records.

It is the responsibility of the site principal investigator and personnel to use continuous vigilance to identify and report deviations within five working days of identification of the protocol deviation, or within five working days of the scheduled protocol-required activity. All deviations must be promptly reported to DMID per the protocol deviation reporting procedures. Protocol deviations must be sent to the local IRB/IEC per their guidelines. The site principal investigator and personnel are responsible for knowing and adhering to their IRB requirements. A completed copy of the DMID Protocol Deviation Form must be maintained in the Regulatory File, as well as in the participant's chart if the deviation is participant specific.

10.1.11 Publication and Data Sharing Policy

10.1.12 Human Data Sharing Plan

This study will be conducted in accordance with the following publication and data sharing policies and regulations: National Institutes of Health (NIH) Public Access Policy. This policy which ensures that the public has access to the published results of NIH-funded research. It requires scientists to submit final peer-reviewed journal manuscripts that arise from NIH funds to the digital archive PubMed Central upon acceptance for publication.

10.1.13 Genomic Data Sharing Plan

Not applicable

10.1.14 Publication

Following completion of the study, the Lead Principal Investigator is expected to publish the results of this research in a scientific journal. Data from the clinical trial may also be presented in CIVICs program seminars and the CIVICs annual meeting, subject to approval by DMID, or

used for publication as determined by the PI in collaboration with the study team and in accordance with DMID data sharing policy and the Clinical Trial Agreement. This study will adhere to the publication and data sharing policies and regulations of the sponsor: NIH Public Access Policy. This policy ensures that the public has access to the published results of NIH-funded research. As such, the final peer-reviewed journal manuscripts will be accessible to the public on PubMed Central no later than 12 months after publication.

10.1.15 Conflict of Interest Policy

The independence of this study from any actual or perceived influence, such as by the pharmaceutical industry, is critical. Therefore, any actual conflict of interest of persons who have a role in the design, conduct, analysis, publication, or any aspect of this trial will be disclosed and managed. Furthermore, persons who have a perceived conflict of interest will be required to have such conflicts managed in a way that is appropriate to their participation in the design and conduct of this trial. DMID has established policies and procedures for all study group members to disclose all conflicts of interest and will establish a mechanism for the management of all reported dualities of interest.

10.2 Additional Considerations

10.2.1 Research Related Injuries

If it is determined by the participating site PI that an injury occurred to a participant as a direct result of the tests or treatments that are performed for this trial, then referrals to appropriate health care facilities will be provided to the participant and his or her parent/guardian. Study personnel will try to reduce, control, and treat any complications from this trial. Immediate medical treatment may be provided by the participating site, such as giving emergency medications to stop immediate allergic reactions due to the study vaccine. No financial compensation will be provided to the participant by NIAID, NIH, or the participating site for any injury suffered due to participation in this trial.

10.3 Abbreviations

AE	Adverse Event
CAPA	Corrective and Preventative Action Plan
CFR	Code of Federal Regulations
CI	Confidence Interval
CMP	Clinical Monitoring Plan
CMS	Clinical Material Services
CRF	Case Report Form
CROMS	Clinical Research Operations & Management Support
CSR	Clinical Study Report
DCC	Data Coordinating Center
DMID	Division of Microbiology and Infectious Diseases
eCRF	Electronic Case Report Forms
FDA	Food and Drug Administration
GCP	Good Clinical Practice
HA	Hemagglutinin

HAI	Hemagglutination inhibition
ICF	Informed Consent Form
ICH	International Council for Harmonization
IEC	Independent or Institutional Ethics Committee
IND	Investigational New Drug Application
IRB	Institutional Review Board
MITT	Modified Intention-To-Treat
MedDRA	Medical Dictionary for Regulatory Activities
MOP	Manual of Procedures
N	Number (typically refers to participants)
NA	Neuraminidase
NAI	Neuraminidase Inhibition
NIAID	National Institute of Allergy and Infectious Diseases
NIH	National Institutes of Health
OHRP	Office for Human Research Protections
PHI	Protected Health Information
PI	Principal Investigator
QA	Quality Assurance
QC	Quality Control
RVP	Respiratory Virus Panel
SAE	Serious Adverse Event
SAP	Statistical Analysis Plan
SMC	Safety Monitoring Committee
SRC	Safety Review Committee
SOA	Schedule of Activities
SOP	Standard Operating Procedure
UP	Unanticipated Problem
US	United States

10.4 Protocol Amendment History

Version	Date	Description of Change	Brief Rationale
2.0	02/11/2022	Minor changes incorporated including: Clarification on date when the study will start, acceptable mechanisms of contraception and co-enrollment of Cohort 4 & 5. The protocol was also further updated for consistency and additional clarifications provided.	The protocol builds in additional conditions that may impact study conduct for further clarity/guidance for clinical sites
3.0	09/07/2022	Minor changes incorporated including: Additional clarification to avoid enrolling individual participants with a history of	The protocol builds in additional clarification to study procedures as well as a decreased sample size given

		wheezing episodes and including a narrower window for study visit 2 related to evaluation of wheezing reported after receipt of study vaccine. Decrease in sample size for Cohort 4 from 45 to 25 with corresponding changes in study schema and Statistical Considerations section. Incorporated study halting criteria if influenza activity is greater than 10% locally or regional ILI activity is high. Other minor edits incorporated including correction of window for receipt of seasonal influenza vaccine (in Schedule of Activities), wording related to dose preparation of IP and evaluation of wheezing.	it does not impact probability of identifying unexpected adverse reactions to study vaccine.
4.0	05/26/2023	Change the timing of and required reviews by the SRC after Cohort 5. Descriptions of the antibody test for neuraminidase antibodies has been changed from NAI, a specific type of assay, to anti-NA, to allow for anti-neuraminidase assays other than NAI	Allow administration of first dose in Cohort 6 after safety data of first dose in Cohort 5 and allow for second doses in Cohort 6 to begin after at least 6 of 8 in Cohort 5 have completed through the third day after their second dose. To accommodate the optimal assay/s to measure antibodies against neuraminidase
5.0	12/7/2023	Minor edits in the study design section indicating Cohorts 5-7 will not be enrolled, clarification of endpoints and removal of ISM language	Changes are made to accommodate FDA and other regulatory bodies requirements given non-enrollment in Cohort 5-7 due to a number of non-safety related contingencies (timelines, budgets, recruiting, and lack of additional vaccine lots).

		
Other changes include more clarity on proposed secondary study objectives and associated secondary and exploratory endpoints. Other minor changes include clarification on anticipated interim analysis and publication plans.
 
Additionally, given the sponsor no longer uses an ISM, ISM language has been removed from the protocol.

--	--	--

11. APPENDIX

11.1 Appendix A – Blood and Fluid Collection Volumes by age group

Table 8: Blood and Fluid Collection volumes by Age

Visit number	1	4 OR 4C	6	Target Volume by Day for Serum OR Whole Blood	Max Volume by Day for Serum OR Whole Blood
Target day	1	29 OR V4+28d	V5+28d		
First day of window	1	26 OR V4+25d	V5+25d		
Final day of window	1	32 OR V4+31d	V5+31d		
Visit Type	Vaccine	Vaccine OR Follow	Follow		
Visit venue	Clinic	Clinic	Clinic		
Procedures	per visit				
Serum Vol. (required for all ages)	5ml			Serum	Serum
Additional Serum Vol.	6mo – 4yo None 5yo - 8yo 5 ml (if possible) 9yo – 17yo 5 ml			6mo-4yo: 5ml 5yo-8yo: 5ml 9yo-17yo: 10ml	6mo-4yo: 5ml 5yo-8yo: 10ml 9yo-17yo:10ml
Whole Blood Vol.	6mo – 4yo 8.5ml (if possible) 5yo – 8yo 8.5 ml 9yo – 17yo 8.5 ml			Whole Blood	Whole Blood
6mo – 4yo	8.5ml (if possible)			6mo-4yo: 0ml 5-8yo: 8.5ml 9-17yo: 17ml	6mo-4yo: 8.5ml 5-8yo: 8.5ml 9-17yo: 17ml
Additional Whole Blood Vol.	6mo – 4yo None 5yo – 8yo None 9yo – 17yo 8.5 ml				
Target Volume by Day	6mo – 4yo 5.0 ml 5yo – 8yo 13.5 ml 9yo – 17yo 27.0 ml			Total Target by Age for study	
6mo – 4yo	5.0 ml			6mo – 4yo – 15ml	
5yo – 8yo	13.5 ml			5yo – 8yo – 40.5ml	
9yo – 17yo	27.0 ml			9yo – 17yo – 81ml	
Max Volume by Day	6mo – 4yo 13.5 ml 5yo – 8yo 18.5 ml 9yo – 17yo 27.0 ml			Total Max by Age for study	
6mo – 4yo	13.5 ml			6mo – 4yo – 40.5ml	
5yo – 8yo	18.5 ml			5yo – 8yo – 55.5ml	
9yo – 17yo	27.0 ml			9yo – 17yo – 81ml	
Non-Blood Sample					
Nasal Lavage	5-10 ml			15-30 ml across all ages for study	

11.2 Appendix B – Evaluation Criteria for Acute Wheezing

The Brighton Collaboration has set forth their recommendations for the evaluation of wheezing following vaccination[20]. This study will, in general, conform with those recommendations.

Definition.

Acute wheeze is the sudden onset of adventitious breath sounds that are high pitched or whistling. They are generated by turbulence of air in the intrathoracic airways due to airflow limitation. Acute wheeze has the following characteristics:

1. The sounds must be of sudden onset (unexpectedly and without warning, leading to a marked change in a participant's previously stable condition).
2. The sounds must be "adventitious" which means extra or additional sounds heard over the participant's normal breath sounds.
3. The sounds must involve high-pitched breath sounds, which may sometimes be "whistling" in nature.
4. The sounds must be audible on auscultation with a stethoscope by a healthcare provider and the sounds must be audible during expiration. (There may also be inspiratory sounds, but there must not be *only* inspiratory sounds.)

Although parents and caregivers of children, or children themselves, may provide the study team or their healthcare providers with complaints they term "wheezing" or other complaints that lead to a healthcare provider diagnosing "acute wheeze", the symptom of "wheezing" or any other symptom that a parent or caregiver of a child, or a child him- or herself, reports or endorses, will not be deemed as adequate to meet the case definition (although it is often the impetus for evaluation by a healthcare provider or the research team).

When all the above criteria have been met, the child will be termed to have definite acute wheeze. When the study team is provided with information after the time when confirmation of acute wheeze is possible, such as at a future research follow-up visit, and the documentation of the episode cannot confirm or deny that it met the criteria, then the investigator, using his/her judgment, may record the event as "possible acute wheeze". For example, a parent states that the child has a respiratory event that led to a health care visit and at the visit the child was given a bronchodilator, but the documentation required to meet the criteria were not recorded or are not available, such an even would be deemed "possible acute wheeze."

Timing.

Enhanced surveillance of episodes of acute wheeze will occur in the 28 days after intranasal administration of study product. During the 28-day period post-vaccination, families will be given instructions to notify the research team immediately for all illnesses, including "wheezing", respiratory symptoms such as cough, sneezing, rhinorrhea, tachypnea, chest indrawing, etc. at each encounter with the study team and via a weekly eDiary check conducted within +/- 3-day window. If symptoms trigger an evaluation, a research clinician will conduct the evaluation, if possible. If an external physician completes the evaluation, data will be retrieved from the medical records of the participant. The evaluation will include a standard set of clinical variables and a respiratory viral panel. Following this period of enhanced surveillance for acute wheeze, the study team will continue to collect information on all reports of wheezing until the end of each child's participation, which spans until the last clinical evaluation of the participant in the following year (April of the following year). During this period, families will be instructed to let the study team know about any wheezing episodes but not all respiratory events, such as rhinorrhea and sneezing. Information on the wheezing events, including respiratory virus panel (RVP) results, if conducted as part of routine care, will be collected via chart abstraction.

Data collection.

For each of these episodes, the participant will have collected, preferably by the research team, but if not possible then by an outside provider, a standard set of variables. If not all the variables are collected by an outside provider, the study team will record the available data. When possible, the research team will evaluate the acute episode. If not all the variables are available, to determine if the event met the criteria for definite acute wheeze, the investigator may report it as possible acute wheeze. If a complete RVP is not available but another microbiologic test was performed and provides an alternate explanation then this will be considered acceptable in lieu of investigator initiated RVP.

Determining whether the episode meets or does not meet the definition.

Episode evaluations will first determine if the definition of definite acute wheeze has been met, as defined above. Variables necessary to make that determination are the following: 1. Acute onset episode (y/n), 2. Auscultation by a healthcare provider using a stethoscope reveals breath sounds that are high-pitched/whistling, adventitious (y/n), and 3. The sounds are heard during expiration (y/n).

Standard set of variables to be collected.

If the definition of acute wheeze is not met, routine collection of AE variables, when in the time frame stated in the protocol for AEs, will be done.

If the definition of acute wheeze *is* met, the following information will be collected, in order to characterize the acute wheeze episode:

1. Date of onset of symptoms that led to evaluation.
2. Date of meeting the case definition of acute wheeze
3. Date when the AE resolves – this will be determined when symptoms resolve and does not require repeat physical exams.
4. Relationship of person reporting the symptoms that prompted evaluation
5. Role (investigator, outside healthcare provider, etc.) of person performing auscultation and respiratory evaluation.
6. Accompanying respiratory findings:
 - a. Respiratory Rate in breaths per minute (graded into normal or tachypneic, by age¹)
¹The upper limit by age is as follows: 6–11mo - 38 breaths/min; 1–3 yo - 30 breaths/min; 4–9yo - 24 breaths/min; 10–13yo - 22 breaths/min; 14–17yo - 20 breaths/min [21]
 - b. Inspiratory: Expiratory ratio (less than or equal to 1:3 [normal] or 1:3 or greater [prolonged])
 - c. Lower chest wall indrawing (yes or no)
 - d. Central cyanosis (yes or no)
 - e. Oxygen saturation by pulse oximetry (actual value and graded as <92% [significant hypoxia] or 92% or more [normal or mildly abnormal])
 - f. Inability or significant difficulty in breastfeeding, drinking, talking, based on age (inability, difficulty, neither)
 - g. Altered mental status/confusion as determined by the healthcare professional (yes or no)
7. Accompanying non-respiratory findings:
 - a. Temperature (including type of thermometer)

- b. Blood pressure (if available)
8. Treatment:
 - a. Type
 - b. Dose
 - c. Duration
9. Outcome
10. Is this an SAE?
11. Exposures other than the investigational product that could potentially be the etiology: infection, environmental, food
12. Results of RVP, including COVID-19 test, or other infectious disease diagnostics performed.

Severity Grades

All episodes of acute wheeze will be graded based on the most severe time point within the single episode. Clinical discretion may be employed to determine when an event is deemed a new event, since signs and symptoms may come and go during a single wheezing event. The grading of the event should be as follows.

Mild = Grade 1 = “Wheeze without respiratory distress or danger signs”. Definition: wheeze only- that is, without any of the additional findings in Grades 2 or 3.

Moderate = Grade 2 = “Wheeze with respiratory distress but without danger signs”. Definition: wheeze plus one or both of the following: lower chest indrawing, I:E > 1:3, but none of the additional findings in Grade 3.

Severe = Grade 3 = “Wheeze with danger signs”. Definition: wheeze plus one or more of the following: oxygen saturation < 92%, central cyanosis, altered mental status/confusion, inability to breastfeed, drink, or speak (depending on age)

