8.1.1.3. Unsolicited Adverse Events

When calculating the incidence of adverse events on the participant-level, each participant will only be counted once at the maximum value of the respective variable (e.g., maximum severity, maximum relatedness, etc.) and any repetitions of adverse events within a participant will be ignored. All adverse events reported will be included in the summaries and analyses.

The number and percentage of participants reporting at least one unsolicited adverse event will be summarized by MedDRA SOC and PT. Denominators for percentages are the number of participants who received the vaccination being summarized where applicable.

The following summaries of AEs will be provided:

- Incidence of the following by severity and relationship to study product
 - Non-serious unsolicited AEs in the 28 days following each study vaccination and across study vaccinations ([Table 40](#) through [Table 50](#))
 - AESIs ([Table 51](#) through [Table 58](#))
 - SAEs ([Table 59](#) through [Table 66](#))
 - NOCMCs ([Table 67](#) through [Table 74](#))
- Bar chart of the incidence of the following by severity of:
 - Non-serious unsolicited AEs in the 28 days following each study vaccination and across study vaccinations ([Figure 34](#) through [Figure 38](#))
 - AESIs ([Figure 39](#) through [Figure 41](#))
 - SAEs ([Figure 42](#) through [Figure 44](#))
 - NOCMCs ([Figure 45](#) through [Figure 47](#))
- Total frequency by severity, relationship to study product, and resolution of:
 - Non-serious unsolicited AEs in the 28 days following each study vaccination and across study vaccinations ([Table 75](#) through [Table 85](#))
 - AESIs ([Table 86](#) through [Table 93](#))
 - SAEs ([Table 94](#) through [Table 101](#))
 - NOCMCs ([Table 102](#) through [Table 109](#))

- Bar chart of frequency by severity of
 - Non-serious unsolicited AEs following each study vaccination and across study vaccinations ([Figure 48](#) through [Figure 52](#))
 - AESIs ([Figure 53](#) through [Figure 55](#))
 - SAEs ([Figure 56](#) through [Figure 58](#)),
 - NOCMCs ([Figure 59](#) through [Figure 61](#))

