Non-serious unsolicited AEs in the 28 days following study vaccination by participant will be presented ([Listing 13](#)). AESIs, SAEs, and NOCMCs occurring during the study period will also be presented ([Table 110](#), [Table 111](#), and [Table 112](#), respectively). Additional information about wheezing events corresponding to vital signs and respiratory virus panels will be presented in [Table 113](#).

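### Appendix B codes an I:E ratio of exactly 1:3 as both normal and prolonged, does not match its own Grade 2 cut-off, and leaves two collected wheeze findings outside the severity grades

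*Protocol*

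**What the plan says.** Protocol 11.2 (Appendix B) first lists what is recorded for an episode that meets the wheeze definition, then gives the severity grades. Item 6 of the list has seven respiratory findings, 6a to 6g. Three matter here:

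- 6a: "Respiratory Rate in breaths per minute (graded into normal or tachypneic, by age"
- 6b: "Inspiratory: Expiratory ratio (less than or equal to 1:3 [normal] or 1:3 or greater [prolonged"
- 6f: "Inability or significant difficulty in breastfeeding, drinking, talking, based on age (inability, difficulty, neither"

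The other four are lower chest indrawing (6c), central cyanosis (6d), oxygen saturation (6e) and altered mental status (6g).

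The grades are:

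- Grade 3: wheeze with at least one of "oxygen saturation < 92%, central cyanosis, altered mental status/confusion, inability to breastfeed, drink, or speak (depending on age"
- Grade 2: "wheeze plus one or both of the following: lower chest indrawing, I:E > 1:3, but none of the additional findings in Grade 3"
- Grade 1: "wheeze only- that is, without any of the additional findings in Grades 2 or 3". Its label says that neither respiratory distress nor danger signs are present.

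SAP 8.1.1.3 asks for "Incidence of the following by severity and relationship to study product", and AESIs are among the events covered (Tables 51–58). It also asks for event counts by severity (Tables 86–93) and severity bar charts (Figures 39–41 and 53–55). It continues: "Additional information about wheezing events corresponding to vital signs and respiratory virus panels will be presented in" Table 113.

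**The concern.** A severity scale should send each recorded pattern of findings to one grade, and two sites with the same child in front of them should reach the same grade. Appendix B does not guarantee this for the I:E ratio, because the collection codes overlap and the grading cut-off follows neither of them cleanly.

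The list of collected findings and the list of graded findings also differ, with no explanation. At stake is the severity profile of the one event singled out because of a theoretical risk of intranasal influenza vaccines (Protocol 8.3.3). Few events are likely to fill those tables, so a single ambiguous episode would be visible.

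**Working it through.** The plan gives no figure to reproduce here. The check is of the rules themselves.

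**1. Which findings can change the grade.** Six of the items are treated as two-level (6a to 6e and 6g), and 6f has three levels. The number of possible profiles is 2⁶ × 3 = 192.

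- Not Grade 3: saturation, cyanosis and mental status all clear, and 6f not *inability*. That leaves 2 (rate) × 2 (I:E) × 2 (indrawing) × 2 (*neither* or *difficulty*) = 16.
- Grade 3: 192 − 16 = 176.
- Grade 1: of the 16, those with no indrawing and no I:E finding, 2 × 2 = 4.
- Grade 2: 16 − 4 = 12.

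Across all 192 profiles, changing the rate from normal to tachypneic never changes the grade, and neither does changing *neither* to *difficulty*. Three of the four Grade 1 profiles carry tachypnea, difficulty or both. These are counts of patterns, not expected frequencies.

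**2. The I:E ratio.** The cut-offs can be read by the length of the expiratory part, or as a quotient (1:2 = 0.500, 1:3 = 0.333, 1:4 = 0.250).

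| I:E | 6b code, expiratory part | Grade 2? | 6b code, quotient | Grade 2? |
|---|---|---|---|---|
| 1:1 | normal | no | prolonged | yes |
| 1:2 | normal | no | prolonged | yes |
| 1:3 | both | no | both | no |
| 1:4 | prolonged | yes | normal | no |
| 1:5 | prolonged | yes | normal | no |

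The overlap at 1:3 appears under both readings. There, an episode may be coded prolonged, yet the strict cut-off makes it Grade 1. A site that grades from the code would call it Grade 2. Item 6b lists only the two categories, whereas 6e asks for the actual value as well as the category. If only the category is kept, 1:3 cannot later be separated from longer expiration. SAP Table 113 heads its column as a ratio without defining it.

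**3. Comparison with the protocol's other scales.** In Protocol Table 4, a sore throat that interferes with eating or drinking is Grade 2 (ages 4–8 and 9–17), and trouble breathing that interferes with daily activity is Grade 2 in all three age bands. The general scale in Protocol 8.4.7.1 puts interference with usual activities at Grade 2. None of these governs wheeze, but significant difficulty drinking without another listed sign is Grade 1 on the wheeze scale.

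**4. Size.** The AESI tables keep the one-dose and two-dose 10⁹ groups of 2–8-year-olds separate, so planned vaccine groups have 15 or 30 children. One regraded event is 1/15 = 6.7 points or 1/30 = 3.3 points. In the all-vaccine tables it is 1/90 = 1.1 points.

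**The case against.** The other side has a good deal of force.

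- A reader might infer that children in respiratory distress are being tabulated as Mild. For this scale, Appendix B ties distress to indrawing or I:E above 1:3. Whether tachypnea or difficulty also amounts to distress is a clinical judgement that the documents do not settle. The appendix says that it broadly follows an external guideline, which cannot be checked here. This stands.
- Collecting a finding does not commit the plan to grading it. Temperature, blood pressure and treatment are also collected and ungraded. This stands, but a label that rules out distress still needs a stated basis.
- A reader might call the I:E coding inverted. That needs the quotient reading. The word prolonged in 6b points to the expiratory part, under which only the overlap at 1:3 remains. This stands, although the direction is nowhere stated.
- A reader might think that feeding and speaking are ignored. They are not: *inability* is a Grade 3 criterion. Only the *difficulty* level is unused.
- A reader might extend the point to the primary endpoint or the halting rules. Endpoint 4 counts participants with an AESI and, unlike endpoints 1 to 3, does not ask for results by grade. The halting criteria in Protocol 7.1.1 use Grade 3 or no grade at all, so the Mild/Moderate boundary feeds none of them.
- Table 113 shows respiratory rate, oxygen saturation and I:E for each wheezing event where available, so tachypnea remains visible. It has no column for indrawing, cyanosis, feeding or speaking, or mental status, so grades cannot be rebuilt from it.

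None of this removes the overlap at 1:3 or its mismatch with Grade 2.

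**Conclusion.** The point holds within limits. The I:E coding is wrong as written: exactly 1:3 has two codes, the grade follows a strict cut-off that does not match the prolonged code, and the direction is left to the reader. Tachypnea and *difficulty* never affect the grade, and the plan does not say why.

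The effect is confined to the AESI severity tables and figures, at 3.3 to 6.7 points per regraded event in a vaccine group and 1.1 points across all 90 vaccinees. These figures assume the planned group sizes and one affected event; the documents give no expected wheeze frequency. The statement that halting is unaffected assumes that the Grade 3 criteria stay as they are. The documents do not support assigning tachypnea or *difficulty* to a particular grade. They support asking that the two parts of Appendix B be reconciled.

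**What to change.** - Reconcile item 6b with Grade 2 by using one non-overlapping code, expressed as how many times longer expiration is than inspiration. To match the present strict Grade 2 wording, prolonged would mean more than three times and normal three times or less.
- Have the sponsor's clinicians state how tachypnea and *difficulty* bear on the grade, or why they do not, and make the Grade 1 label agree.
- In SAP Table 113, show the expiratory multiple, and add indrawing, cyanosis, feeding or speaking, and mental status where available.
- Add a check in the SAP of the entered grade against the recorded findings, with queries for disagreements.

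The cost is wording and programming, because every item is already specified for collection. There are two drawbacks. Data from outside providers, and from record review or parental report after 28 days, may be incomplete, so some grades will not be checkable. A few events may also be regraded after enrollment has ended. The SAP says that it is finalized before individual unblinding of the pharmaceutical partner and principal investigator (4.5.5), and that interim safety was shown by cohort only (5.6.1). The clarification should therefore be recorded before that unblinding. If it comes later, the entered and checked grades should be shown side by side.
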